after haemodialysis with a washout period of ≥ 7 days in-between. Infusion of the first dose was completed 4 hours before haemodialysis (predialysis). The infusion of the second dose was started at least 60 minutes after the end of haemodialysis (postdialysis). Subjects with normal renal function received a single dose of 400 mg ceftaroline fosamil infused intravenously over 1 hour. Plasma levels of ceftaroline fosamil were substantially higher in subjects with ESRD than subjects with normal renal function, which may be due to the same arm being used for PK sampling and intravenous infusion. The systemic exposure (AUC) was significantly greater in subjects with ESRD than in subjects with normal renal function for both ceftaroline (89% predialysis; 167% postdialysis) and ceftaroline M-1 (231% predialysis; 573% postdialysis). In subjects with ESRD dosed with ceftaroline fosamil before haemodialysis, the $t_{1/2\lambda_z}$ was significantly longer for both ceftaroline (123%) and ceftaroline M-1 (2-fold) in subjects with ESRD dosed before or after haemodialysis than in subjects with normal renal function, but the time to maximum concentration (t_{max}) was similar among the treatments. Results of the study showed that haemodialysis could remove ceftaroline and ceftaroline M-1 from plasma.

For further information, please refer to the Investigator's Brochure.

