After a washout of at least 1 week, patients will be admitted to the study centre on Day -1 for Period 2 and will receive a single intravenous dose of 200 mg ceftaroline fosamil infused over 1 hour on Day 1, prior to the haemodialysis session. Haemodialysis will then start 15 minutes after the end of the infusion, within a ± 5 minutes time window. Samples of blood and dialysate will be collected for up to 48 hours after the start of the infusion for the determination of ceftaroline fosamil, ceftaroline, and ceftaroline M-1. Blood samples will also be collected at specified time points for haematocrit and endogenous markers including blood urea nitrogen and creatinine. Patients will remain in the study centre until the completion of the study procedures on Day 3. The study design for Group 1 is presented in Figure 1.

[figure not shown]
Figure 1 Study design for Group 1

Group 2 (healthy volunteers)

After screening, eligible healthy volunteers will be admitted to the study centre on Day -1 and will receive a single intravenous dose of 600 mg ceftaroline fosamil infused over 1 hour on Day 1. Blood will be collected for up to 24 hours after the start of infusion for the determination of ceftaroline fosamil, ceftaroline, and ceftaroline M-1. The healthy volunteers will remain at the study centre until the completion of the study procedures on Day 2. The study design for Group 2 is presented in Figure 2.

Figure 2 Study design for Group 2

Throughout the treatment periods, subjects will be monitored for safety and blood samples for the PK evaluation will be collected.

The schedule of assessments and the PK sampling time points are provided in [Table 2](#) and [Figure 3](#), respectively.

Table 2 Schedule of assessments

Assessment	Screening	Residential period/ treatment period ⁿ				Follow-up
	Day -28 to -2	Day -1	Day 1	Day 2	Day 3	7-10 days after discharge
Informed consent ^a	X					
Inclusion/exclusion criteria	X	X				
Demographics	X					
Medical, surgical, and smoking history	X					
Luteinising hormone/follicle-stimulating hormone ^b	X					
Estimated creatinine clearance ^c	X	X		X ⁱ	X ⁱ	
Hepatitis B, hepatitis C, and HIV	X					
Alcohol and urine drug screen	X	X				
Clinical chemistry and haematology ^b	X	X			X	X
Urinalysis/urine microscopy ^d	X	X				X
Pregnancy test ^e	X	X				X
Physical examination		X			X	
Brief physical examination						X
Height, weight, and BMI calculation ^f	X	X				X
12-Lead electrocardiogram ^g	X	X				X
Admission to study centre		X				

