^d All blood samples collected during and surrounding the haemodialysis session will be collected from both predialyser and postdialyser lines. At each timepoint, the pre- and postdialyser samples should be collected as close as possible in the following sequence: predialyser PK, predialyser BUN/creatinine, postdialyser PK, and post dialyser BUN/creatinine samples. The postdialyser sample should be collected within 1 minute of the respective predialyser sample.

^e The blood samples during haemodialysis session, including protocol times 90 minutes, 2.25 hour, 3.25 hour, and 4.25 hour, should be collected at 15 minutes, 1 hour, 2 hours, and 3 hours after the start of

haemodialysis, respectively; the 5.25 hour (4 hours after start of haemodialysis) samples must be collected just at the end of the haemodialysis session.

- f Dialysate will be collected in appropriate containers over 1 hour intervals throughout the entire (approximately 4 hours) haemodialysis session (including, 0 to 1, 1 to 2, 2 to 3, 3 to 4 hours after the start of haemodialysis). The blood flow, dialysate flow rate, dialysate volume, type of dialysis membrane, and the make and model of the dialyser will be recorded. The entire dialysate will be collected, its volume recorded, and the primary and backup samples retained for analysis of ceftaroline and ceftaroline M-1 concentrations.

BUN: blood urea nitrogen; PK: pharmacokinetic.

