In Study P903-18, blood samples for plasma concentrations of ceftaroline fosamil, ceftaroline, and ceftaroline M-1 were collected up to 72 hours after start of investigational product administration (ESRD patients had PK draws up to 48 hours during predialysis period and up to 72 hours during after-dialysis period and normal subjects had PK draws up to 48 hours after start of infusion). In ESRD patients dosed before dialysis, 5 of 6 patients had no measurable ceftaroline concentrations at 48 hours postdose. In ESRD patients dosed after dialysis, 4 of

6 patients had measurable ceftaroline concentrations in the 48-hour sample; concentrations dropped to below the lower limit of quantification (BLQ) in all 6 patients at the 60-hour and 72-hour time points. There were no detectable concentrations in the 24-, 36-, and 48-hour samples of the healthy control volunteers. For ceftaroline M-1, in ESRD patients dosed before dialysis, all 6 patients had no measurable concentrations at 48 hours postdose. In ESRD patients dosed after dialysis, 3 of 6 patients had measurable concentrations in the 60-hour sample; ceftaroline M-1 concentrations dropped to BLQ for all 6 patients at the 72-hour time point. In healthy controls, 1 of 6 volunteers had a measurable M-1 concentration in the 24-hour sample and there were no detectable concentrations at the 36- and 48-hour time points. Considering the times of last measurable ceftaroline and ceftaroline M-1 concentrations, the washout period of at least 1 week for ESRD patients in the current study is adequate. In addition, the difference in PK sampling durations for ESRD patients (up to 48 hours) and healthy volunteers (up to 24 hours) is not expected to have a confounding effect on differences in $t_{1/2\lambda_z}$, if observed.

As the PK of the ceftaroline-related moieties has been shown to be linear, a single dose of ceftaroline fosamil is considered adequate to define the PK behaviour of ceftaroline fosamil, ceftaroline, and ceftaroline M-1. Mathematical projections from single dose to steady-state conditions will be used to develop administration guidelines for this group of patients.

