11.2 Calculation or derivation of pharmacokinetic variables

Pharmacokinetic analyses of the plasma concentration data for ceftaroline fosamil (the prodrug of ceftaroline), ceftaroline, and ceftaroline M-1 (the metabolite of ceftaroline) and of ceftaroline and ceftaroline M-1 concentrations in dialysate will be performed at Quintiles Inc., Overland Park, Kansas, USA. Quintiles Standard Operating Procedures and Work Instructions will be used as the default methodology if not otherwise specified. The actual sampling times (in unit of hour) will be used in the plasma PK parameter calculations.

Pharmacokinetic parameters will be derived using noncompartmental methods with WinNonlin[®] Professional Version 5.2, or higher, (Pharsight Corp., Mountain View, California, USA). All PK computations will be performed using WinNonlin[®] Professional Version 5.2, or higher; or SAS[®] Version 9.2, or higher (SAS Institute Inc., Cary, North Carolina, USA).

For missing samples or samples collected close to but not exactly at the end of the infusion, ceftaroline fosamil concentrations at the end of infusion will not be imputed unless warranted by the data. If a concentration of ceftaroline fosamil at the end of infusion needs to be estimated, the imputation will be in accordance with procedures described in Quintiles Standard Operating Procedures. The decision to impute a missing end of infusion value will be made on a case-by-case basis and documented in the CSR. In brief, the estimation steps are as follows:

1. Analyse the concentration-time data using an intravenous bolus model by setting the end of infusion time as the dosing time
2. Back-extrapolate the concentration at the time of dosing (ie, the end of infusion concentration)
3. Augment the original concentration-time data set by inserting the back-extrapolated end of infusion concentration
4. Process the augmented data set with an intravenous infusion model

Any imputed values for ceftaroline fosamil will solely be used for PK parameter calculations and will not be included in any summary or inferential statistics. Imputed values will be reported in the CSR. Imputations for the end of infusion concentrations will not be performed for ceftaroline and ceftaroline M-1.

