Where possible, the PK parameters listed below will be derived. For Group 1/Period 2 samples collected during the haemodialysis, only predialyser concentrations will be included in the analyses, unless otherwise indicated. Other parameters may also be calculated if deemed appropriate. The molecular weights to be applied in the PK calculations are 684.7 for ceftaroline fosamil, 604.7 for ceftaroline, and 622.7 for ceftaroline M-1.

The following plasma PK parameters will be determined for ceftaroline fosamil, ceftaroline, and ceftaroline M-1 in Group 1 (both Periods 1 and 2) and Group 2:

- Maximum plasma concentration (C_{\max} , $\mu\text{g/mL}$)
- Time to maximum concentration (t_{\max} , h)
- Area under the plasma concentration-time curve from zero to infinity (AUC, $\mu\text{g}\cdot\text{h/mL}$)
- Area under the plasma concentration-time curve from zero (ie, start of infusion) to time of the last quantifiable concentration ($\text{AUC}_{(0-t)}$, $\mu\text{g}\cdot\text{h/mL}$)
- Area under the plasma concentration-time curve from zero to 12 hours after the start of the infusion ($\text{AUC}_{(0-12)}$, $\mu\text{g}\cdot\text{h/mL}$)

- Terminal rate constant (λ_z , 1/h)
- Terminal half-life ($t_{1/2\lambda_z}$, h), determined as $\ln(2)/\lambda_z$
- Dose-normalised C_{max} , AUC, $AUC_{(0-t)}$, and $AUC_{(0-12)}$
- C_{max} ratio of ceftaroline/ceftaroline fosamil and ceftaroline M-1/ceftaroline ($MR_{C_{max}}$) (adjusted for differences in molecular weights)
- AUC ratios of ceftaroline M-1/ceftaroline (MR_{AUC}) (adjusted for differences in molecular weights)

In addition, the following plasma PK parameters will be calculated for ceftaroline and ceftaroline fosamil in Group 1 (both Periods 1 and 2) and Group 2:

- Mean residence time (MRT, h)
- Total body clearance of drug from plasma (CL for ceftaroline fosamil, apparent CL for ceftaroline [L/h])
- Volume of distribution based on the terminal phase (V_z for ceftaroline fosamil, apparent V_z for ceftaroline [L])
- Volume of distribution at steady-state (V_{ss} for ceftaroline fosamil, apparent V_{ss} for ceftaroline [L])

The following parameters will be calculated for ceftaroline and ceftaroline M-1, unless otherwise noted, in Group 1 Period 2 only:

- Area under the plasma concentration-time curve from 75 minutes to 5.25 hours after the start of the infusion ($AUC_{(1-5)}$, $\mu\text{g}\cdot\text{h}/\text{mL}$)

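### Vz, Vss and MRT of ceftaroline are ordered noncompartmentally for the dialysis period, where clearance is not constant, so both volumes come out too high with no change in distribution

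*Protocol*

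**What the plan says.** Protocol Section 11.2 states the method for every period: "Pharmacokinetic parameters will be derived using noncompartmental methods with WinNonlin". It then lists MRT, CL, Vz and Vss, which "will be calculated for ceftaroline and ceftaroline fosamil in Group 1 (both Periods 1 and 2) and Group 2". The synopsis lists the same parameters under all subjects, with no exception for the dialysis period.

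Section 3.1 sets the timing in Period 2: "Haemodialysis will then start 15 minutes after the end of the infusion, within a ± 5 minutes time window". Dialysate is collected "over 1 hour intervals throughout the entire (approximately 4 hours) haemodialysis session" (notes to Figure 4). For samples drawn during the session, "only predialyser concentrations will be included in the analyses, unless otherwise indicated" (Section 11.2), so the dialysis-phase concentrations form part of the profile.

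The reporting filters in Section 11.2 are a minimum of three points for lambda_z, an Rsq above 0.80, and no more than 20% of AUC extrapolated. Section 12.2.3 summarises parameters by analyte, group and period. Section 3.2 adds: "Mathematical projections from single dose to steady-state conditions will be used to develop administration guidelines for this group of patients".

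**The concern.** Vz = CL/lambda_z and Vss = CL x MRT are distribution volumes only if clearance is constant over the whole profile. Period 2 breaks that condition by design. CL = Dose/AUC averages over on- and off-dialysis time, while lambda_z reflects the time after dialysis. Their ratio therefore rises when dialysis removes drug, even if distribution is unchanged. Vss and MRT are affected for a related reason.

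The Period 2 values would be tabulated beside valid Period 1 and Group 2 values, and would suggest that dialysis enlarges ceftaroline's volume of distribution. The filters do not screen for this: simulated Period 2 profiles had an Rsq of about 1 and about 1% to 2% extrapolated area (assuming an LLOQ of 0.05 µg/mL).

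There is also a labelling problem. Section 11.2 calls Dose/AUC total body clearance, apparent for ceftaroline. In Period 2 it already contains dialysis clearance, and a reader who adds CL_D to it counts dialysis twice.

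**Working it through.** **Inputs from the Protocol.** Molecular weights are 684.7 (prodrug) and 604.7 (ceftaroline), from Section 11.2. The earlier ESRD study recovered 76.5 mg, stated as 21.6% of a 400 mg dose, in a 4-hour session (Section 13.2). Its AUC excess over controls was "for both ceftaroline (89% predialysis; 167% postdialysis", and ceftaroline half-life was 123% longer (Section 1.1). Normal half-life is 2 to 3 h (Section 1.1).

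**The plan's own figure.** 400 x 604.7/684.7 = 353.3 mg, and 76.5/353.3 = 21.66%. The stated 21.6% reproduces to rounding.

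**Identities.** With dose in ceftaroline equivalents, mass balance gives Dose = CL_body x AUC + A_D. Hence:
- Dose/AUC = CL_body + A_D/AUC, a mean total clearance for the session.
- (Dose - A_D)/AUC = CL_body.
- In one compartment with lambda_z taken after dialysis, Vz/V = 1/(1 - fD), with fD as a fraction.
- Since Vss = CL x MRT, Vss/V = MRT/(V/CL), so Vss and MRT carry the same relative error.

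**Size from the Protocol's figures alone (earlier study, same lambda_z in both periods).**
- From recovery: 1/(1 - 0.216) = 1.28.
- From the AUCs: 2.67/1.89 = 1.41.

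The two inputs disagree, so the range is Vz +28% to +41%.

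**Size in this study.** Assumptions: one compartment, 1-hour infusion, immediate prodrug conversion, and an ESRD half-life of 2.23 x (2, 2.5, 3 h) = 4.46, 5.58, 6.69 h. The dialysis rate constant kd is solved so that a 4-hour session recovers 21.66%. Section 1.1 puts the earlier session 4 h after the end of infusion (5 h after its start) and Section 13.2 puts it 4 h postdose, so both were tried. The session is then moved to 1.25 to 5.25 h.

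| ESRD half-life (h) | Earlier session start (h) | kd (1/h) | fD here | Vz/V | Vss/V | MRT by NCA (h) | Period 2 V/CL (h) |
|---|---|---|---|---|---|---|---|
| 4.46 | 4 | 0.165 | 33.2% | 1.497 | 1.227 | 5.27 | 4.30 |
| 4.46 | 5 | 0.206 | 38.8% | 1.634 | 1.266 | 4.99 | 3.94 |
| 5.58 | 4 | 0.134 | 30.5% | 1.438 | 1.249 | 6.99 | 5.59 |
| 5.58 | 5 | 0.158 | 34.5% | 1.527 | 1.289 | 6.79 | 5.27 |
| 6.69 | 4 | 0.117 | 28.8% | 1.404 | 1.260 | 8.66 | 6.87 |
| 6.69 | 5 | 0.134 | 31.9% | 1.469 | 1.295 | 8.51 | 6.57 |

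**Fourth row in full.** Assume a normal clearance of 100 mL/min = 6.0 L/h; the Protocol says only that it is close to GFR, and the ratios above do not depend on it.
- CL_body = 6.0/2.67 = 2.247 L/h; k = ln 2/5.575 = 0.1243 per h; V = 2.247/0.1243 = 18.1 L.
- Period 2 CL = 2.247 x 1.527 = 3.43 L/h.
- Vz = 3.43/0.1243 = 27.6 L (+53%); Vss = 3.43 x 6.79 = 23.3 L (+29%).
- Check on clearance: dose 176.6 mg, A_D = 0.3452 x 176.6 = 61.0 mg, AUC = 176.6/3.43 = 51.5 mg·h/L. Then (176.6 - 61.0)/51.5 = 2.24 L/h, which returns CL_body to rounding.
- Double counting: CL_D = 0.158 x 18.1 = 2.86 L/h. True on-dialysis clearance is 2.247 + 2.86 = 5.11 L/h; adding CL_D to Period 2 CL gives 6.29 L/h, 23% too high.

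The same method applied to a Period 1 profile returns the true CL and volumes. Illustrative two-compartment runs gave Vz +56% to +80% and Vss +33% to +42% relative to Period 1.

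**The case against.** The strongest case on the other side is that little depends on these values. The primary objective is served by Period 1 and Group 2, where CL, Vz, Vss and MRT are valid, and by CL_D = A_D(1-5)/AUC(1-5), which is sound. Period 2 Cmax, AUCs, A_D, fD and E are unaffected. The analysis is descriptive, the planned exposure figures use only Cmax, AUC and AUC(0-t), and Section 3.2 does not say which parameters feed the steady-state projections. All of this stands and it limits the severity. It does not make the Period 2 volumes right.

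Three stronger readings are tempting, and the Protocol does not support them.
- *Period 2 clearance is an artefact.* It is not. Dose/AUC is the AUC-weighted mean total clearance for that session, and body clearance is recoverable from data already planned. Only the label needs work.
- *MRT is biased downward.* Period 2 MRT is 10% to 22% below Period 1, but dialysis really does shorten residence: V/CL falls by 29% to 39% (for example 6.87 h against 9.65 h, and 3.94 h against 6.43 h). The error is upward.
- *The lambda_z window in Period 2 is a defect.* Five samples follow dialysis (8, 12, 24, 36 and 48 h), and the regression interval and number of points are listed for each profile. Selection of points may properly sit in an SOP or the SAP.

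**Conclusion.** The point holds for ceftaroline Vz, Vss and MRT in Group 1/Period 2. The documents' own figures for the earlier study put the overstatement of Vz at 28% to 41%, taking the same lambda_z. For this study's schedule the one-compartment range is Vz +40% to +63%, Vss about +23% to +29%, and MRT about 23% to 29% above that period's V/CL. These projections rest on the assumed half-lives, the one-compartment form and the calibration to the earlier recovery; the direction follows from the design.

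Period 2 CL stands as a number, but needs a label saying that it includes dialysis. A reader might infer that the primary objective or the dosing projections are compromised. The Protocol does not show that, because valid Period 1 values exist for both. Severity is moderate to minor.

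**What to change.** In Section 11.2 and the synopsis:
- Restrict Vz, Vss and MRT of ceftaroline to Group 1/Period 1 and Group 2.
- Keep Period 2 CL, labelled as mean total clearance including dialysis, with a note that CL_D must not be added to it.
- Add non-dialysis clearance in Period 2 as (Dose x 604.7/684.7 - A_D(1-5))/AUC. This treats any loss of intact prodrug into the dialysate as negligible, since the prodrug is not assayed there.
- State that the volume used in any steady-state projection comes from Period 1.

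Period 2 Cmax, AUCs, A_D, fD, E and CL_D stay as planned. The cost is wording in two places and the matching table shells. No samples, assays or subjects are added.

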2. STUDY OBJECTIVES

2.1 Primary objective

To characterise the PK of ceftaroline after intravenous infusion of ceftaroline fosamil in patients with ESRD and a matched control population with normal renal function and to characterise the clearance of ceftaroline by haemodialysis.

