6.4.1 Collection of samples

Blood samples (approximately 4 mL per sample) for determination of ceftaroline fosamil (the prodrug of ceftaroline), ceftaroline, and ceftaroline M-1 (the metabolite of ceftaroline) concentrations in plasma will be taken contralaterally from the dosing arm at the times presented in the study plans, [Figure 3](#), and [Figure 4](#). The date and time of collection of each blood sample will be recorded. In addition, for Group 1/Period 2 only, the sampling location (predialyser or postdialyser) will be recorded for all blood samples collected during and surrounding the haemodialysis session.

In Group 1/Period 2 only, blood samples will be taken at specified time points for haematocrit and endogenous markers including blood urea nitrogen and creatinine. Dialysate will be collected over 1-hour intervals throughout the entire haemodialysis session (approximately 4 hours). The blood flow, dialysate flow rate, dialysate volume, type of dialysis membrane, and the make and model of the dialyser will be recorded. For each collection interval, the entire dialysate will be collected, its volume and collection start/stop date recorded, and the primary and backup samples retained for analysis of ceftaroline and ceftaroline M-1 concentrations.

Samples will be collected, labelled, stored, and shipped as detailed in Laboratory Manual.

For blood volume see [Section 7.1](#).

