- Amount of drug extracted unchanged into the dialysate (A_D , mg) during each 1-hour interval, cumulatively, and overall ($A_{D(1-5)}$, mg) for the entire haemodialysis session (time: 75 minutes to 5.25 hours after the start of infusion)
- Percent of dose recovered in dialysate (f_D , %) during each 1-hour interval, cumulatively, and overall ($f_{D(1-5)}$, %) for the entire haemodialysis session (time: 75 minutes to 5.25 hours after the start of infusion); adjusted for the molecular weight differences as follows:

– Ceftaroline

$$f_D, \% = 100 \times (A_D / [\text{Dose} \cdot 604.7 / 684.7]) \text{ or}$$

$$f_{D(1-5)}, \% = 100 \times (A_{D(1-5)} / [\text{Dose} \cdot 604.7 / 684.7])$$

– Ceftaroline M-1

$$f_D, \% = 100 \times (A_D / [\text{Dose} * 622.7 / 684.7]) \text{ or}$$

$$f_{D(1-5)}, \% = 100 \times (A_{D(1-5)} / [\text{Dose} * 622.7 / 684.7])$$

- Extraction coefficient (E) at each time point during haemodialysis will be calculated for ceftaroline fosamil, ceftaroline, and ceftaroline M-1 as follows:

$$(C_a - C_v) / C_a$$

where, C_a and C_v are the predialyser and postdialyser plasma concentrations, respectively.

In addition, E will be calculated for the endogenous markers blood urea nitrogen and creatinine.

- Haemodialysis clearance (CL_D , L/h) of ceftaroline and ceftaroline M-1 will be calculated from both recovery data (primary method) as well as based on Fick principle (secondary method):

– Primary method: $CL_D = A_{D(1-5)} / AUC_{(1-5)}$

– Secondary method: $CL_D = Q * (1 - Hct) * E$

where, Q is the flow rate of blood through the dialyser, Hct is the averaged haematocrit values obtained at predose and 8 hours postdose (relative to the start of the infusion), and E is extraction coefficient. For the purpose of this calculation, distribution into red blood cells is assumed to be negligible and blood to plasma conversions are based on haematocrit only.

The following PK parameters of each analyte will be calculated for diagnostic purposes and listed but not summarised for plasma data in all groups and periods:

- The time interval (λ_z upper and lower) of the log-linear regression to determine λ_z
- Number of data points (λ_z , N) included in the log-linear regression analysis to determine λ_z . A minimum of 3 data points will be used
- Coefficient of determination for calculation of λ_z (Rsqr). If Rsqr is 0.80 or less, λ_z and related parameters will not be reported

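### The secondary (Fick) haemodialysis clearance formula omits fluid removed across the dialyser, so it leaves out part of the clearance whenever net fluid is removed

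*Protocol*

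**What the plan says.** Part of the primary objective (Section 2.1) is "to characterise the clearance of ceftaroline by haemodialysis". Section 11.2 gives two calculations for ceftaroline and for ceftaroline M-1. The primary method divides the total amount recovered in dialysate, A_D(1-5), by the plasma AUC(1-5) over the session. The other is written "Secondary method: $CL_D = Q * (1 - Hct) * E", and the text adds that "Q is the flow rate of blood through the dialyser, Hct is the averaged haematocrit values obtained at predose and 8 hours postdose".

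E is the concentration ratio (Ca − Cv)/Ca, "where, C_a and C_v are the predialyser and postdialyser plasma concentrations, respectively". Section 11.2 declares two simplifications for this calculation: "distribution into red blood cells is assumed to be negligible and blood to plasma conversions are based on haematocrit only". Neither concerns fluid lost across the dialyser.

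On data collection, Figure 4 footnote f says: "The blood flow, dialysate flow rate, dialysate volume, type of dialysis membrane, and the make and model of the dialyser will be recorded". Section 6.4.1 gives the same list and adds that "the entire dialysate will be collected, its volume and collection start/stop date recorded". Neither place lists an ultrafiltration rate or volume, and the protocol does not mention ultrafiltration elsewhere.

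**The concern.** The formula multiplies inlet plasma flow by a concentration ratio. That equals the removal rate divided by Ca only if outlet plasma flow equals inlet plasma flow. When water is drawn off in the dialyser, less plasma leaves than enters, and the drug remaining in it is more concentrated than it would otherwise be. E alone then understates the amount removed.

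The recovery method does not share this limit, because drug carried across with the removed fluid is in the collected dialysate. The two estimates can therefore differ for a reason that lies in the formula. The gap would vary between patients according to how much fluid each has removed, and between ceftaroline and M-1 according to their extraction. With 8 patients planned in Group 1 and at least 6 expected to complete, such a gap would be hard to explain afterwards if fluid removal had not been recorded.

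A later analysis plan could change the formula, but it could not supply a reading that was never taken.

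**Working it through.** **Plan's own figure.** There is none to reproduce. The protocol states no blood flow, E, ultrafiltration rate or expected CL_D for this study.

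**Mass balance on the plasma side.** Let Qp = Q × (1 − Hct) be inlet plasma flow and Quf the net fluid removal rate.

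- Drug in per minute: Qp × Ca
- Drug out per minute: (Qp − Quf) × Cv
- Removal rate divided by Ca: [Qp × Ca − (Qp − Quf) × Cv]/Ca. Since Cv/Ca = 1 − E, this equals Qp × E + Quf × (1 − E).

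The protocol's formula is the first term only, which is the special case Quf = 0. Since E lies between 0 and 1, the omitted term is not negative.

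Relative shortfall = Quf × (1 − E) / [Qp × E + Quf × (1 − E)].

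**Inputs.** The session length of about 4 hours is from Section 6.4.1. Q = 300 mL/min, Hct = 0.35, and the values of E and of fluid removed are assumptions. Hct 0.35 is consistent with the entry requirement of more than 30%. Then Qp = 300 × 0.65 = 195 mL/min.

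| Fluid removed over 4 h | Quf (mL/min) | E | Qp × E | Quf × (1 − E) | Full CL_D (mL/min) | Shortfall |
|---|---|---|---|---|---|---|
| none | 0 | any | 195 × E | 0 | 195 × E | 0% |
| 1 L | 1000/240 = 4.17 | 0.6 | 117.0 | 1.67 | 118.67 | 1.4% |
| 2 L | 2000/240 = 8.33 | 0.5 | 97.5 | 4.17 | 101.67 | 4.1% |
| 3 L | 3000/240 = 12.5 | 0.3 | 58.5 | 8.75 | 67.25 | 13.0% |

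**Range.** Over an assumed grid (Q 200 to 400 mL/min, Hct 0.31 to 0.40, E 0.2 to 0.8, Quf 4 to 16 mL/min) the shortfall runs from 0.4% to 35%. The lowest value comes from high flow, high E and little fluid removed: 0.8/(276 × 0.8 + 0.8) = 0.4%. The highest comes from the opposite corner: 12.8/(120 × 0.2 + 12.8) = 35%.

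**Effect of the averaged haematocrit.** A one-compartment simulation of a 4-hour session compared the protocol's secondary value with A_D/AUC. It took two cases for the averaged haematocrit: the 8-hour value back at baseline, and the 8-hour value still raised. At Quf = 0 the two methods agreed exactly. At Quf = 10 mL/min, the secondary value relative to the primary was:

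- E 0.2: −15% to −17%
- E 0.5: −3.1% to −5.6%
- E 0.8: +0.3% to −2.3%

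The positive value arises when the 8-hour haematocrit has returned to baseline. The average then misses the rise during the session and overstates plasma flow, which offsets the omitted term.

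**Can fluid removal be derived from what is recorded?** In principle it is effluent volume minus dialysate flow × time. At an assumed dialysate flow of 500 mL/min, 30 L passes per hour, so a 1% flow error is 0.3 L. Removing 2 L over 4 hours is 0.5 L per hour, so the error would be more than half the quantity sought. Body weight is no substitute, because Table 2 and Section 6.3.6 schedule it only at screening, Day -1 and follow-up.

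**The case against.** The strongest reply is that this is an undeclared simplification in a secondary, descriptive parameter, and that one sentence saying ultrafiltration is neglected would be enough. Several parts of that reply stand.

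- **The premise is not in the documents.** That these patients have fluid removed during scheduled dialysis is an assumption, though a reasonable one for patients dialysed 3 to 4 times per week. Without fluid removal the formula is exact.
- **The size is modest in most cases.** It is a few percent at moderate to high extraction. With an assumed between-patient CV of 20%, the standard error of a mean from 6 to 8 patients is 20/√8 = 7% to 20/√6 = 8%, larger than the 1.4% and 4.1% cases. Nothing in the protocol points to extraction as low as 0.3. Section 1.1 describes about 20% protein binding and no distribution into erythrocytes.
- **No comparison rule exists.** The protocol nowhere makes the Fick value a formal check on the recovery value. Misreading a gap as red-cell uptake is unlikely, given what Sections 1.1 and 11.2 say about red cells.
- **The added term does not repair the haematocrit approximation.** In the +0.3% case, adding the term (2/156 = 1.3% at Q 300, Hct 0.35, E 0.8, Quf 10) would move the secondary value to about +1.6%.

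These points limit the size and consequence of the error, but they do not make the formula right when fluid is removed. The standard-error comparison concerns between-patient noise, whereas the omitted term has one sign and does not average out across patients. A statement that ultrafiltration is neglected would disclose the simplification, but it would leave no direct reading with which to correct it.

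**Conclusion.** The point holds in a conditional form. Whenever net fluid is removed during the session, the secondary formula omits Quf × (1 − E), which the recovery method captures. The size rests on assumed values throughout: about 1% to 4% at E of 0.5 to 0.6 with 1 to 2 L removed over 4 hours, about 13% at E 0.3 with 3 L removed, and zero with no fluid removal.

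Three stronger readings are not supported.

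- A reader might infer that the secondary estimate is low in every patient and must disagree with the primary. The documents give no fluid removal rate, and at high E the averaged haematocrit can offset the omission.
- A reader might infer that the gap has nothing to do with the drug. Its cause is fluid removal, but its size depends on each analyte's own extraction, so it can differ between ceftaroline and M-1.
- A reader might infer that the primary clearance result is compromised. It is not: the recovery CL_D does not use this formula.

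The change is still worth making, because the clearance concerned is named in the primary objective and the correction is cheap.

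**What to change.** In Section 11.2, change the secondary method to CL_D = Q × (1 − Hct) × E + Quf × (1 − E). Take Quf from the collection interval that contains or ends at each E time point. The 15-minute and 1-hour values then use the first interval, and the 2-, 3- and 4-hour values use the second, third and fourth.

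In Figure 4 footnote f and Section 6.4.1, add the net ultrafiltration volume for each 1-hour collection interval, read from the dialysis machine, to the data recorded. Dividing it by the interval length gives Quf.

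Keep recovery as the primary method.

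The cost is one extra recorded value per hour and one extra term in the formula. No samples or visits are added, and the dialysis itself does not change. The haematocrit approximation remains, so some residual difference between the methods at high extraction should still be expected.
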